- 3. The ability of older adults to maintain or improve muscle health may be associated with systemic indicators of the effects of aging on immune function.** Age-related decline in functions of the immune system results in a weaker response to vaccination [10], diminished ability of immune cells to proliferate, and problems that specifically affect muscle. Acute increases in cytokines after exercise initiate muscle repair [11], but with aging inflammation becomes chronic and detrimental. For example, inflammation induces muscle catabolism in rats [12] and is associated with sarcopenia and functional decline in humans [13]. Thus, systemic differences in immune parameters between older adults may reflect ability to improve or maintain muscle health.
- 4. Cells of the immune system residing in muscle play a central role in the developing model of muscle adaptation to exercise.** Macrophages transition between three functional phases in response to exercise. Phase 1 is an inflammatory response mediated by cytokines which initiate muscle repair and clear debris from damaged myofibers [14]. After this initial cleanup, Phase 2 is a down-regulation of inflammation by anti-inflammatory cytokines so that secondary damage does not occur. This allows the muscle to become conducive to growth [15]. In the regenerative Phase 3, macrophage arginine metabolism increases and promotes cell growth [16] and growth factors are produced to further stimulate myogenesis [17]. As muscle adapts to training, macrophage function may then become dedicated to producing growth factors required for hypertrophy.

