*****See Next Page for Figure*****

A. Influence of Aging on IGF1 mRNA levels

B. TIMP1 Response to Exercise

[figure not shown]

[figure not shown]
Figure 4: Influence of aging and exercise on muscle mRNAs. A. IGF1 mRNA is lower in muscle of old than young adults before and after exercise ($P<0.05$). Box plots denote the medians (line), 25th and 75th percentiles (boxes), 10th and 90th percentiles (whiskers), and outliers (dots). B. TIMP1 mRNA increases in muscle of young ($P<0.05$) but not old adults after exercise. Median (triangle) and individual subject responses (line) are shown.

Finding 4: Muscle expression of genes associated with inflammation, growth, and remodeling is strongly correlated in older adults with muscle size and strength gained from resistance training [3].

Study: Older (61-78 yrs) men (N=3) and women (N=5) completed 12-weeks of high-intensity progressive resistance training of the thigh muscles. Biopsies were collected prior to training and analyzed by real-time PCR and immunohistochemistry. Muscle size change range from -1% to +18% while strength increase ranged from +8% to +65%. Strength gain correlated ($R > 0.7$, $P < 0.05$) with expression of mRNAs encoding cytokines (IL1 β , IL10, IL1RA), growth (CNTF, GDF8, IGF1, IGFBP5) and remodeling factors (MMP2, TIMP1). The result is shown for IGF1 in Figure 5A. Strength gain also correlated with the number of CD163+ macrophages in muscle with the exception of one outlier (Figure 5B). Similar results were found for muscle size.

Conclusions: Macrophages and mRNAs associated with inflammation, growth, and remodeling appear to be involved with adaptation to exercise in older adults. However, these variables could be covariates affected by an unknown determinant of muscle adaptation. The proposed study will allow investigation into whether macrophage function or immune function in general influences adaptation to resistance training in older adults.

A. IGF1 versus Strength Gain

B. CD163 Macrophage Number versus Strength Gain

[figure not shown]
[figure not shown]

Figure 5. Relationship between baseline molecular and cellular measures for muscle of older adults and percent strength gain for knee extension after 12-weeks of training. A. Pearson correlation for IGF1 mRNA and strength gain (triangles = males, circles = females). B. Relationship between number of muscle macrophages and strength gain.

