H. Additional Signaling Pathway Members: The regulation of inflammation and growth in macrophages and muscle cells is regulated by a complex network of signaling molecules. Thus, in addition to NF κ B and PI3K, other factors will also be measured for effects of supplementation and exercise [24;25;64]. Of main interest are FOXO1, STAT3, AKT, S6K, and ERK1 and 2. The activity of these factors is regulated, in part, by their phosphorylation state. Matched antibody pairs are available to measure the ratio of these phosphorylated to un-phosphorylated proteins by Western Blot (Cell Signaling Technology, Boston, MA). Pathway scanning kits are also available which include other related molecules in the cascade. Muscle remains from the nutritional supplement pilot study presented in the introduction. This muscle will enable an initial broad assessment of the signaling pathways affected by nutritional supplementation. The results will guide any changes in the specific factors chosen for assay in muscle collected for the proposed study.

I. Satellite Cells and Myonuclei: Muscle adapts to resistance training through increases in satellite cell numbers and addition of nuclei to the myofiber [21]. However, these adaptations are diminished in older adults [22]. The study will determine if 15-weeks of supplementation increases the number of satellite cells and myonuclei per myofiber in muscle. Satellite cells (Pax7+, CD56+, DAPI+) and myonuclei (Dystrophin plus DAPI staining) will be counted using established staining methods [21].

J. Fiber Size: Muscle also adapts to resistance training by muscle fiber hypertrophy. However, this growth is hindered in individuals, particularly older adults, who have a diminished satellite cell and myonuclei response to training [22]. The study will determine if 15-weeks of supplementation increases the effects of resistance training on myofiber size. Changes in fiber size will be

measured microscopically as the average percent increase in fiber cross-sectional area from baseline to post-training.

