STATISTICAL PLAN: The sample size (N=50) provides greater than 80% power for Aims 1-3 to detect mean differences between groups of 0.8 to 0.85 standard deviation (SD) units at a 5% level of significance. Power calculations were based on using a one-sided t-test to compare independent groups using data from our work and others [2;23;65] though non-parametric tests or transformations will be used as necessary for data containing outliers. There is no formal plan to adjust for multiple comparisons. However, multiple correlation analysis will be used to determine the correlation between endpoints and any possible inflation in the overall Type I error rate. This analysis will allow testing of the overall hypothesis that measures of immune function (Aim 1) will be positively correlated with adaptations to exercise (Aim 2) and retention of muscle strength, mass, and function after exercise training is halted (Aim 3). The hypotheses are stated for each aim and the time points for comparison are listed in Table 6.

Aim 1 Power: Aim 1 will determine if the supplement consumption for 2-weeks improves baseline measures of immune function or the immune responses to vaccination or acute exercise. The representative measures chosen to calculate power are change in muscle macrophage content after exercise (Finding 2) and change in CRP levels post-supplementation (Pilot Study Finding 1). Przybyla et al detected a 29% increase in CD163+ macrophages in young subjects after exercise but no change in older subjects [2]. Power for this aim is calculated to detect at least a 29% greater increase in macrophages in the supplement than the placebo group. Przybyla et al used a nonparametric test to lessen the effects of outliers. To be more conservative here, the calculations here dropped the most extreme high and low data values before estimating effect sizes. With that approach, the 29% increase corresponds to an effect size of 0.8 SD units (mean/SD = 0.128/0.159). Similar results were found using CRP data from Pilot Finding 1. The effect size for change in CRP is 0.85 SD units (mean/SD = 0.665/0.780 for log-transformed data). Having at least 20 subjects per group will provide 80% or greater power to detect a mean shift of 0.8-0.85 SD units at a significance level of 5% for the following Aim 1 hypotheses:

- a. The response to vaccination will be greater in the supplement than the placebo group. The change between times K and A (Table 6) will be compared between groups.

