- f. The proliferative capacity of peripheral blood mononuclear cells will be greater in the supplement than the placebo group. The change between times G and C will be compared between groups. The change between times I and E will also be compared between groups.
- g. The resting number of muscle CD163+ macrophages will increase in the supplement but not in the placebo group. The change between times H and D will be compared between groups.
- h. The number of muscle CD163+ macrophages will increase after acute exercise in the supplement but not in the placebo group. The change between times J and H will be compared to change between times F and D for both groups.
- i. Resting NFkB activity will decrease and PI3K activity will increase in the supplement group but not in the placebo group. The change between time points H and D will be compared between groups.
- j. In response to acute exercise, NFkB activity will be lower and PI3K activity will be greater in the supplement group than in the placebo group. The change between times J and H will be compared to change between times F and D for both groups. *Responses similar to NFkB are predicted for FOXO1, and responses similar to PI3K are expected for STAT3, AKT, P38 MAPK, and ERK 1 and 2.*

Aim 2 Power: Aim 2 will determine whether supplement consumption increases muscle adaptation to 12-weeks of resistance training. The representative response measure for this objective is post-training percent increase in muscle strength. In a similar study, Trappe et al sought to improve strength gain by resistance training plus drug treatment. The drug treatment group gained significantly more strength by 25.1% than the group receiving placebo (26.4% vs. 21.1%, $P<0.05$) [23]. The previous findings presented here (Finding 4) indicate that older subjects completing a 12-week training program but not taking supplements will experience an average strength gain of $25 \pm 8\%$. If treatment with the proposed supplement improves strength similarly to the Trappe drug treatment, subjects in the supplement group will improve strength by an average of 31% (i.e., 25.1% greater than those of the placebo group). This translates to an approximate effect size of 0.8 SD units ($0.25*0.251/0.08$) if variances are pooled for the groups compared. With 20 subjects per group, there will be 80% power to detect a mean shift of 0.8 SD units using a significance level of 5% for the Aim 2 hypotheses:

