- a. The amount of strength gained from 12-weeks of training will be greater in the supplement than the placebo group. The change between times L and B will be compared between groups.
- b. The amount of muscle size gained from 12-weeks of training will be greater in the supplement than the placebo group. The change between times L and B will be compared between groups.
- c. The increase in muscle function after 12-weeks of training will be greater in the supplement than the placebo group. The change between times L and B will be compared between groups.
- d. The increase in muscle satellite cells after 12-weeks of training will be greater in the supplement than the placebo group. The change between times M and D will be compared between groups.
- e. The increase in muscle myonuclei after 12-weeks of training will be greater in the supplement than the placebo group. The change between times M and D will be compared between groups.
- f. The increase in muscle fiber size after 12-weeks of training will be greater in the supplement group than the placebo group. The change between times M and D will be compared between groups.

Aim 3 Power: Aim 3 will determine if supplement consumption increases the retention of exercise-derived benefits post-training during 26 weeks of long-term follow-up. The representative response measure for this objective is the strength gain retained during long-term follow-up after exercise training is completed. Lemmer et al observed an average gain in muscle strength of 27% ($P<0.01$) in older men after strength training which is similar the 25% gain presented here in Finding 4 [65]. However, at

31-weeks of post-training follow-up, strength had decreased to be about 9% above pre-training levels. Assuming the same level of variation among our subjects in retention of strength gain as the observed 8% SD for strength gain in Finding 4, then a 0.8 SD effect size would be about 6.4% ($0.8*0.08$), translating to our supplement group retaining strength of 12.4% above pre-training levels. With 20 subjects per group, there will be 80% power to detect a mean shift of 0.8 SD units using a significance level of 5%. If the SD for retention of strength is smaller than 8%, then we will have higher power to detect the same difference or equal power to detect smaller differences for the following Aim 3 hypotheses:

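### The immune–muscle correlations are not adjusted for baseline muscle status, so a marker related to baseline strength can correlate with gain through the choice of scale alone

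*Combined protocol and SAP*

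**What the plan says.** The opening paragraph of the Statistical Plan says that "multiple correlation analysis will be used to determine the correlation between endpoints". It states the overall hypothesis as: "measures of immune function (Aim 1) will be positively correlated with adaptations to exercise (Aim 2"), and extends it to the retention outcomes of Aim 3. It gives no model, no outcome scale and no baseline covariate.

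The scale appears in other places:

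- **Strength, Aim 2 Power:** "The representative response measure for this objective is post-training percent increase in muscle strength".
- **Strength, Aim 2 hypothesis a:** "The amount of strength gained from 12-weeks of training will be greater in the supplement than the placebo group", followed by "The change between times L and B will be compared between groups". This does not say whether the change is absolute or percent.
- **Finding 4, Figure 5:** baseline markers are plotted against "percent strength gain for knee extension after 12-weeks of training".
- **Fiber size, Muscle Measures item J:** the change is "measured microscopically as the average percent increase in fiber cross-sectional area from baseline to post-training".

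The Abstract promises multivariable testing across the three aims. Item 14b of the Human Subject Aspects lists medications and medical conditions as possible confounders. Neither names baseline strength. Item 10e provides two strength tests before training.

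**The concern.** The correlation is an observational comparison inside a randomised trial. The discussion of the pilot vaccination results relies on it to draw conclusions even if the supplement does not change immune function. Baseline strength can differ systematically between subjects with high and low marker values, and the design does nothing to prevent that.

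The protocol gives some reason to expect such a relation. Background item 3 says that inflammation "is associated with sarcopenia and functional decline in humans".

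Percent gain is (L − B)/B, with B the baseline and L the post-training value. If absolute gain L − B is unrelated to B, weaker subjects have larger percent gains. Any marker that is higher in weaker subjects then correlates positively with percent gain, and any marker that is higher in stronger subjects correlates negatively. At stake is the interpretation of the mechanistic result: an association could be reported that only reflects baseline strength, or a real one could be masked.

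**Working it through.** **The plan's own figure.** Aim 2 effect size: 0.25 × 0.251 / 0.08 = 0.784, rounded in the plan to 0.8 SD. A one-sided two-sample t-test with 20 per group at 5% has 79.9% power at 0.8 SD, which reproduces the stated 80%. That figure concerns the arm comparison and does not change here.

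**Inputs for the correlation.** From the documents: 40 completers (50 randomised, 20% dropout) and a mean strength gain of 25%. Assumed, because the documents do not give them: baseline CV 20–30%, gain CV 40–60%, and a marker–baseline correlation ρ of −0.3 to −0.5. The marker has no direct link to gain.

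**First-order formula.** If absolute gain G is independent of baseline B, the correlation of the marker with G/B is about −ρ × CV_B / √(CV_B² + CV_G²).

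- Weakest case: 0.3 × 0.20 / √(0.04 + 0.36) = 0.06 / 0.632 = 0.095.
- Strongest case: 0.5 × 0.30 / √(0.09 + 0.16) = 0.15 / 0.5 = 0.30.

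If gain is instead proportional to baseline, percent gain is independent of B and the artefact moves to absolute gain, with the same size and the opposite sign.

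**Simulation** (n = 40, lognormal baseline, one-sided 5% test in the direction of the artefact):

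| True gain model | Scale analysed | Spurious r | Rejection |
|---|---|---|---|
| Absolute, independent of baseline | Percent | 0.09 to 0.28 | about 14% to 57% |
| Absolute, independent of baseline | Absolute | 0 | about 5% |
| Proportional to baseline | Percent | 0 | about 5% |
| Proportional to baseline | Absolute | −0.09 to −0.28 | about 14% to 57% |
| Either | Log post on log baseline + arm + marker | about 0 | about 5% |

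**Direction.** Under the first row, a marker coded so that higher means better function and goes with greater strength has the same r with a negative sign. Rejection in the direction the plan predicts (positive) is then only 0.03% to 1.3%.

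**Sensitivity to the spread of percent gain.** The plan uses 8 points as the SD. Finding 4 reports gains from +8% to +65% in 8 subjects, and 8 values with that range cannot have an SD below 57/√14 = 15.2. If the 8 is a standard error, the SD is 8 × √8 = 22.6. This assumes that both figures describe the same strength measure. With baseline CV 20–40%, absolute gain independent of baseline and a two-sided 5% test:

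- Target SD 8 points: spurious r of 0.19 to 0.49, rejection 24% to 92%. The target is met only at CV 20%; at 30% and 40% the denominator alone produces SDs of 8.2 and about 11.6.
- Target SD 22.6 points: r of 0.07 to 0.25, rejection 7.5% to 35%.

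**The case against.** Five points count on the other side.

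- **The scale is not fixed.** The percent measure for strength comes from a power justification, and the tested hypothesis leaves the scale open. This stands: among the planned outcomes, only fiber size is defined as a percentage. An open scale does not remove the problem, because each scale carries the artefact under one of the two gain models.
- **Proportional gain is plausible.** Item 10e sets loads at 60–80% of each subject's own maximum and retests about every sixth session. If gain follows baseline, percent gain is clean. This also stands, and it means that moving to absolute gain would not be a safe remedy.
- **The sign may oppose the hypothesis.** A reader might infer that the artefact would falsely confirm the overall hypothesis. The documents do not support that in general. The plan treats a pro-inflammatory state as poor function, so if weaker subjects are more inflamed, measures of good function are pushed towards a negative correlation with percent gain. Only counting inflammation itself as a favourable predictor, as the positive cytokine correlations in Finding 4 might suggest, gives false confirmation.
- **The marker–baseline link is assumed.** No document gives its size. Many Aim 1 measures are changes (K versus A, G versus C, H versus D), which may relate less to baseline strength than resting levels do.
- **Finding 4 is not explained away.** A reader might infer that its correlations are an artefact. It reported R above 0.7 for nine mRNAs in 8 subjects; under the assumptions above, the chance of r > 0.7 at n = 8 is about 4% to 10% per marker. Four of those mRNAs are lower in older muscle under Finding 3. If they are also lower in weaker subjects, the artefact would push them negative.

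**Conclusion.** The concern holds in a limited form. The analysis that carries the overall hypothesis has no stated scale and no baseline adjustment, and under either scale a marker related to baseline strength can correlate with gain for that reason alone. The size depends on assumptions outside the documents: 0.09 to 0.28 in the main illustration, and none if the scale happens to match the true gain model. The direction depends on the marker, so the result may be a spurious association or a masked one.

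Three stronger readings are not supported: that every immune marker will correlate with percent gain, that Finding 4 is shown to be an artefact, and that the supplement–placebo comparison is biased. In that comparison, baseline strength is balanced in expectation by randomisation.

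**What to change.** State the outcome scale and model for the immune–muscle associations in the SAP before analysis:

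- For strength, muscle area and fiber size, regress the log post-training value on the log baseline value, arm and the immune measure, and report the partial correlation for the immune measure. Leaving the log-baseline slope free accommodates both gain models. Keep percent gain for description.
- Average the two pre-training strength tests as the baseline, since measurement error in a single test leaves residual confounding.
- For bounded scores such as the Berg scale, and for cell counts that may be zero, use an untransformed or rank-based model with the baseline as covariate.
- For Aim 3, use the value at time L as the baseline covariate, since those changes start there.

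The cost is SAP wording and one or two degrees of freedom per model. No new data are needed.
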